9.1.3 Safety Endpoints

Toxic Death (TD): Any death that is not clearly related to disease progression or to external causes (e.g. accident) that occurs during protocol therapy or during recovery following protocol therapy, or prior to commencing subsequent non-protocol course of therapy, will be considered a toxic death for the purposes of this study.

9.2 Study Design

An open label design over two Marqibo® dose levels will be used to evaluate its substitution for vincristine in three different treatment cohorts: (A) patients treated with UK ALL R3, (B) patients treated with UK ALL R3 that omits Mitoxantrone, and (C) patients treated with a modified ALL maintenance regimen. Prior data on relapse ALL patients treated with standard UK ALL R3 and with COG protocol therapies (section 2.3) suggest that approximately 10% of patients treated in first relapse will experience grade 3 or higher toxicity sufficient to prevent the start of subsequent therapy by day 49. Data from patients treated in second or greater relapse, which will represent

the majority of patients on this study, suggest higher delay rates, but are imprecise due to the small number of patients.

For Cohort A, the original design criteria for escalation to DL2 ($\leq 2/6$ not successfully treated at DL1) has been satisfied. Hence, following Amendment #2, a minimum of 6 and a maximum of 12 patients (including 6 for expansion) who are evaluable for the primary endpoint will be enrolled at DL2. Following Amendment #3, Cohort A was dose de-escalated to DL1 given the development of two DLTs at DL2.

Since treatments in Cohorts B and C were expected to be less toxic than Cohort A, as detailed below Cohorts B and C initially opened to accrual at DL2.

For Cohort B, dosing began at DL2. The cohort was subsequently de-escalated to DL1 after 2 patients were enrolled. The decision to dose de-escalate was an elective decision made by the study committee in the context of known hepatic toxicity associated with Marqibo®, the development of hepatic DLT in one subject on this cohort, and a second subject who was close to meeting criteria for DLT based on hepatic function tests. Cohort B will remain open to accrual at DL1 with 6-12 evaluable patients. Cohort B may be re-escalated to DL2 pending further experience at DL1 ($\leq 2/6$ not successfully treated in the first 6 evaluable patients).

For Cohort C, dosing began at DL2. Cohort C will remain open to accrual at DL2 with 6-12 evaluable patients, provided the primary endpoint conditions are met, ie, $\leq 2/6$ not successfully treated in the first 6 evaluable patients at this dose level. If Cohort C is de-escalated, the cohort may continue to accrue at DL1 between 6 to 12 evaluable patients at that dose level.

The occurrence of unsuccessful treatment, following the definition in Section 9.1.1, will be monitored in real time during the Phase I and expansion accruals. The design will not be prescriptive. Rather, if at any time after the third patient is enrolled either within a single cohort or in all cohorts combined, if nominally more than 1/3 of evaluable patients within a single cohort or in all cohorts combined are not successfully treated the study will be suspended pending review by the study committee of the types and severity of toxicities in all three cohorts, with possible determinations to continue at the specified dose level in all three cohorts, to de-escalate the dose of Marqibo® to DL1 in one or more cohorts, or to halt the study in one or more or cohorts, with appropriate amendments as necessary. In addition, during Phase I, the decision to de-escalate will be considered separately for each cohort and dose level when more than 1 patient is treated unsuccessfully after the first 6 evaluable patients have been enrolled. And the decision to escalate during Phase I will be considered separately for each cohort and dose level when no more than 1 patient is treated unsuccessfully after the first 6 evaluable patients have been enrolled. Accrual to the study will be halted, before reopening for expansion, once at least 6 evaluable patients have been treated at the final tested dose level in each of the three cohorts.

Treatment success, as defined in in Section 9.1.1, during the first course of treatment will continue to be monitored during the expansion. Assuming a treatment failure rate that exceeds 10% (i.e., $p_0 > 0.10$) is unacceptable, a Bayesian monitoring rule based on a pessimistic Beta (1,4) prior distribution will be used to judge the empirical evidence from both the Phase I and expansion

cohorts. This prior has mean 0.20, median 0.16, and 90% of support under 0.48. A posterior probability of greater than 80% that $p_0 > 0.10$ will be considered statistical evidence that the treatment failure rates may exceed 10%. Operationally, this criterion will be satisfied if 2 or more of the first 5 evaluable patients in the expansion cohort experience a treatment failure as defined by the protocol, and subsequently, if 3 or more of the first 6 evaluable patients have a treatment failure. If this criterion is satisfied, the study will be suspended to accrual pending review of toxicities by the study committee, in consultation with the Data and Safety Monitoring Committee, to determine whether the study should continue as planned, be amended, or be terminated.

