4.2 Dose Limiting Toxicity

Toxicity will be graded using the CTCAE criteria, version 4.03. The CTCAE provides descriptive terminology and a grading scale for each adverse event listed. A copy of the CTCAE can be downloaded from the CTEP home page (<http://ctep.cancer.gov>). Any dose-limiting toxicity (DLT) should be reported immediately through the TACL Operations Center to the Study Chair or Vice Chair. In addition to CTCAE, grading of sensory and motor neuropathies will be augmented by definitions listed in Appendix 5.

4.2.1 Definition of DLT: Dose limiting toxicity (DLT) will be defined as the occurrence of non-hematologic DLT and/or hematologic DLT as defined below.

4.2.1.1 Non-hematological DLT:

(Cohorts A and B) Any Grade 3 or greater non-hematological toxicity that is possibly, probably or definitely attributable to the protocol regimen and prevents a patient from receiving the required number of doses of therapy (as specified in Section 9.0) or from proceeding with further therapy by day 49 of the treatment cycle.

(Cohort C) Any Grade 3 or greater non-hematological toxicity that is possibly, probably or definitely attributable to the protocol regimen and prevents a patient from receiving the required number of doses of therapy (as specified in Section 9.0) or from proceeding with further therapy by day 21 of the treatment cycle for Stratum C.

4.2.1.2 Hematological DLT:

(Cohorts A and B) The absence of peripheral blood count recovery (ANC >500/ μ L and platelet count > 20,000/ μ L) 7 weeks (49 days) after the start of chemotherapy in the absence of persistent leukemia or documented myelosuppressive infection. Subjects with abnormal blood counts (Grade 1 through 4) at baseline due to disease will not be evaluable for hematologic DLT and will be considered not having had hematologic DLT for the purposes of the definition in 4.2.1.

(Cohort C) The absence of peripheral blood count recovery (ANC > 500/ μ L and platelet count > 20,000/ μ L) 3 weeks (21 days) after the start of chemotherapy in the absence of persistent leukemia or documented myelosuppressive infection. Subjects with abnormal blood counts (Grade 1 through 4) at baseline due to disease will not be evaluable for hematologic DLT and will be considered not having had hematologic DLT for the purposes of the definition in 4.2.1.

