9.3 Patient Evaluability

9.3.1 Definition of a patient evaluable for the primary endpoint

A patient will be considered evaluable for the treatment success endpoint (section 9.1.1) if (s)he receives any portion of treatment, except if treatment or follow-up is terminated for reasons unequivocally unrelated to treatment toxicity (e.g., if a drug is omitted from the regimen for reasons aside from toxicity, or treatment is terminated because of problems unequivocally related to disease progression). Patient who are not evaluable for the primary endpoint will be replaced.

9.3.2 Definition of a patient evaluable for toxicity:

Any patient who receives at least one dose of any drug on study will be considered evaluable for toxicity.

9.3.3 Definition of a patient evaluable for response:

A patient will be considered evaluable for response if the patient receives all or part of protocol therapy and the patient is under follow-up for a sufficient period to evaluate the disease at the end of protocol therapy or to meet the definition of progressive disease. A patient who dies as a result of toxicity after receiving all or part of protocol therapy, or who is removed from therapy for problems possibly related to disease progression, will be considered a non-responder.

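### Escalation (now live only for Cohort B) and reopening for expansion can rest on six evaluable patients whose treatment outcomes are not yet settled

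*Combined protocol and SAP*

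**What the plan says.** Section 9.2 (Study Design) says escalation during Phase I will be considered by cohort and dose level "when no more than 1 patient is treated unsuccessfully after the first 6 evaluable patients have been enrolled". De-escalation uses the mirror condition, "when more than 1 patient is treated unsuccessfully after the first 6 evaluable patients have been enrolled". Accrual stops ahead of expansion "once at least 6 evaluable patients have been treated at the final tested dose level in each of the three cohorts". No condition on outcomes is given for reopening.

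Section 9.3.1 defines who counts: "A patient will be considered evaluable for the treatment success endpoint (section 9.1.1) if (s)he receives any portion of treatment". The exception is treatment or follow-up ended for reasons clearly unrelated to toxicity, and such patients are replaced. There is no minimum follow-up. Section 9.3.3, on evaluability for response, does ask for enough follow-up to assess disease.

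Under Section 9.1.1, failure means a DLT, or too few doses for reasons that may involve toxicity. Section 4.2.1 lets part of the DLT definition run to the end of a window. For Cohorts A and B, count recovery is judged "7 weeks (49 days) after the start of chemotherapy in the absence of persistent leukemia or documented myelosuppressive infection", and the non-hematologic criterion asks whether further therapy could proceed by day 49. For Cohort C both limits are day 21.

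Section 9.0 confines Cohort A to dose level 1, has Cohort C already at dose level 2, and leaves escalation possible for Cohort B. An earlier paragraph of Section 9.2 lets Cohort B return to dose level 2 if at most 2 of its first 6 evaluable patients at dose level 1 are not successfully treated.

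**The concern.** The escalation count is tied to enrolment and evaluability, but the event counted can take up to seven weeks to appear. Nothing in the supplied text staggers entry, requires the window to be complete or says how a pending patient is scored. A committee following the sentence could therefore compare a failure count from three or four known outcomes with a limit meant for six. That error runs one way, towards escalating.

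The decision at stake is whether Cohort B returns to dose level 2. That is the level at which Section 9.2 reports a hepatic DLT in one of the cohort's two patients, a second patient close to the DLT criteria, and two DLTs in Cohort A. Reopening for expansion has the same gap, because the six need only have been treated.

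**Working it through.** **Nothing to reproduce.** The plan gives no operating characteristics for these rules, so the check is a direct calculation.

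**Inputs.**
- Limits of at most 1 failure and at most 2 failures among 6 evaluable patients (both in Section 9.2).
- Illustrative true failure rates p. Section 2.3 reports delay beyond day 49 in 6 of 16 patients (38%) in second or later relapse, and calls 45% unable to proceed by day 49 unacceptable. These are delay rates rather than the full failure endpoint. I add 40% as a value between them.
- Assumption: k of the 6 outcomes are known, and the 6 − k pending patients have shown no failure so far. The documents do not give k, so a range is shown.

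**Formula for the at-most-1 rule.** With independent patients, P(rule met) = (1 − p)^k + k·p·(1 − p)^(k−1).

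At p = 0.40:
- k = 6: 0.0467 + 0.1866 = 0.233
- k = 5: 0.0778 + 0.2592 = 0.337
- k = 4: 0.1296 + 0.3456 = 0.475
- k = 3: 0.2160 + 0.4320 = 0.648

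At p = 0.45:
- k = 6: 0.0277 + 0.1359 = 0.164
- k = 3: 0.1664 + 0.4084 = 0.575 (0.57475 unrounded, so 57%)

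| True failure rate | 0 pending | 1 pending | 2 pending | 3 pending |
|---|---|---|---|---|
| 38% | 0.266 | 0.372 | 0.510 | 0.677 |
| 40% | 0.233 | 0.337 | 0.475 | 0.648 |
| 45% | 0.164 | 0.256 | 0.391 | 0.575 |

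**What the excess means.** Under the assumption, the gap from the first column is the probability that the interim count permits escalation although the final six contain 2 or more failures. With three pending at 45% it is 0.575 − 0.164 = 0.411.

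**The other Cohort B limit.** For at most 2 failures at p = 0.45, the chance is 0.442 with all six known. With three pending it is 1 − 0.45³ = 1 − 0.0911 = 0.909. The timing gap therefore matters under either limit. The limits themselves differ substantially with complete data: 0.442 against 0.164 at 45%.

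**The suspension rule.** It applies "after the third patient is enrolled either within a single cohort or in all cohorts combined" and acts "if nominally more than 1/3 of evaluable patients within a single cohort or in all cohorts combined are not successfully treated". Two known failures give:
- 2/3 = 67%, 2/4 = 50% and 2/5 = 40%: each suspends.
- 2/6 = 33.3%: does not exceed one third.

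The sixth case therefore escapes only if the second failure becomes known after the sixth patient has been dosed. If only failed or completed patients were counted, one early failure with two patients pending would read 1/1 = 100% and suspend, where the present rule reads 1/3 and does not.

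**The case against.** The strongest reply is that the text sets an earliest time, not a deadline. Section 9.2 calls the design non-prescriptive and says decisions will be considered. DLTs are to be reported immediately (Section 4.2), and safety review is weekly as needed (Section 12.2). The committee moved Cohort B down after two patients, by what Section 9.2 calls an elective decision. The Cohort B paragraph does not use the word enrolled and can be read as meaning six observed outcomes. All of this stands. It shows that the committee could wait, but nothing requires it to.

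The size can also be challenged. Missed doses and many toxicities show early. A patient who recovers and starts further therapy before day 49 is settled early. Patients with disease-related abnormal baseline counts are deemed free of hematologic DLT, although the non-hematologic test still applies to them. Accrual may be slow: the study was activated in July 2016, and Section 9.2 reports the Cohort A escalation criterion as met in connection with Amendment 2, dated July 2018. If so, one pending patient is more plausible than three, and at 40% the comparison is 34% against 23%. That is an inference, because Sections 2.4.1 and 2.4.2 on experience to date are not in the supplied text.

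A reader might infer more than the documents support:
- **That escalation may occur on the day the sixth patient enrols.** The six must be evaluable, so some treatment must have been given, and evaluability can later be lost.
- **That no outcome is known before day 49.** Some failures and some successes are.
- **That the one-third rule is broken and needs a completed-patient denominator.** That change would count early failures at once while successes wait, which is the opposite bias.
- **That the de-escalation sentence needs the same edit.** Requiring complete windows there would only delay action on failures already known.

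**Conclusion.** The point holds for escalation and for reopening after the accrual halt. As written, both can proceed on unsettled outcomes, and the resulting error favours escalation. It does not hold as a general fault in the monitoring rules.

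The tabulated probabilities are upper bounds. They assume independent patients, no failures yet seen among pending patients, and one to three pending at the decision. None of these is stated in the plan. That pending patients count as non-failures follows from the literal wording; the plan does not say it. Because the rule is discretionary and one escalation path remains, this is a should-fix matter.

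**What to change.** In the Section 9.2 escalation sentence, and in the matching Cohort B paragraph, require that each of the six evaluable patients has a settled outcome. Settled means one of three things: the patient has failed; has already met the success definition (minimum doses received, DLT criteria resolved, further therapy able to proceed); or has completed the day-49 window (day 21 in Cohort C). A patient who loses evaluability is replaced, and the replacement must also be settled.

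Make the same condition the requirement for reopening accrual for expansion. The halt itself can stay keyed to patients treated, since stopping early does no harm.

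Reconcile the two Cohort B limits, at most 2 of 6 and at most 1 of 6, so that one applies.

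Leave the de-escalation sentence and the one-third denominator unchanged, so that known failures still act at once. Showing the number of pending patients beside the one-third rate would let the committee see how firm it is.

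The cost is an amended paragraph or two and a wait of up to 7 weeks after the sixth patient starts treatment (up to 3 weeks for Cohort C), less when outcomes settle early.

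Severity: should-fix.

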Cohort C: Modified Maintenance with Marqibo® (Days 1-14)

Cycle 1	Day 1	Day 2	Day 3	Day 4	Day 5	Day 8	Daily through day 13	Day 14
Marqibo®	●							Response Evaluation
Dexamethasone	●	●	●	●	●			
Methotrexate (PO)	●					●		
Mercaptopurine (PO)	●	●	●	●	●	●	●	
IT Methotrexate as needed no more than once weekly								

Option to repeat Cycle 1 of Cohort C for a second cycle. Cycle 2 may start on Day 15 – 22 of Cycle 1.

Marqibo Dose Levels

Dose Level 1: 1.5 mg/m²

Dose Level 2: 2.0 mg/m²

As of Amendment 3, cohorts A and B will be treating at dose level 1; Cohort C will be treating at dose level 2. Dose level may be modified as per guidance in the statistical section and sites will be appropriately notified if a change will be made.

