9.0 STATISTICAL CONSIDERATIONS

The Phase I sample size for each dose level and each of the three cohorts is 6 evaluable patients for the primary endpoint, consistent with the sample size typically sufficient to demonstrate regimen tolerability in Phase I trials. The maximum sample size in any cohort at a particular dose level is 12 evaluable patients, including 6 evaluable patients for expansion.

As of Protocol Amendment #3, Cohort A will enroll at DL1 only. Cohort B will utilize DL1 and Cohort C will continue treatment at DL2. Dose escalation for Cohort B and de-escalation for Cohort C may still occur per study design.

The focus of the study design and statistical analysis is to determine whether Marqibo® can be substituted for standard vincristine and successfully administered to patients with relapsed ALL in three different treatment cohorts: (A) treatment with the UK ALL R3 regimen; (B) treatment with UK ALL R3 regimen without mitoxantrone, and (C) treatment with ALL maintenance therapy. Secondary objectives include estimating rates of serious toxicities and therapy delays in each of these cohorts. Achievement of response and achievement of an MRD undetectable status will only be evaluated in Cohorts A and B, as Cohort C is not being used to eradicate disease, rather is only intended for the purposes of disease stabilization.

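### Section 9.2 sets two different conditions for re-escalating Cohort B from DL1 to DL2, and they disagree at exactly 2 of 6 patients not successfully treated

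*Combined protocol and SAP*

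**What the plan says.** The decision is still open. Section 9.0 states: "Dose escalation for Cohort B and de-escalation for Cohort C may still occur per study design". The dose-level note in the Experimental Design Schemas sends sites to the same part of the protocol: "Dose level may be modified as per guidance in the statistical section".

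Section 9.2 then gives two conditions.

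- **Cohort B paragraph:** "Cohort B may be re-escalated to DL2 pending further experience at DL1". The bracketed condition is at most 2 of the first 6 evaluable patients not successfully treated.
- **General Phase I paragraph**, applied separately to each cohort and dose level: escalation is considered "when no more than 1 patient is treated unsuccessfully after the first 6 evaluable patients have been enrolled", and de-escalation is considered "when more than 1 patient is treated unsuccessfully after the first 6 evaluable patients have been enrolled".

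Both use the treatment-success endpoint of section 9.1.1. Both count the first 6 evaluable patients, which section 9.0 gives as the Phase I size for each cohort and dose level. The general paragraph also says that the design is not prescriptive. It suspends the study for review if nominally more than one third of evaluable patients, in one cohort or in all combined, are not successfully treated.

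**The concern.** Suppose Cohort B has 2 of its first 6 evaluable DL1 patients not successfully treated. The cohort paragraph says that the condition for DL2 is met. The general paragraph puts the same result outside its escalation range and on its de-escalation side. No visible sentence ranks the two.

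The decision is a dose increase in patients aged 1 to 21. Section 9.2 records that Cohort B left DL2 after 2 patients had been enrolled, one with a hepatic DLT and one close to meeting the DLT criteria. The committee, the DSMC and the IRBs should be able to read one condition for going back to that dose.

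**Working it through.** The plan states no operating characteristics for the escalation rule, so there is no figure of its own to reproduce. The check has three parts.

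**1. The two conditions at each count (Cohort B, DL1, first 6 evaluable)**

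| Not successfully treated | Cohort B paragraph | General paragraph |
|---|---|---|
| 0 or 1 | DL2 allowed | escalation considered |
| 2 | DL2 allowed | escalation not put under consideration; de-escalation clause applies |
| 3 or more | condition not met | escalation not put under consideration; de-escalation clause applies |

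They differ on escalation only at 2. DL1 is the lowest listed level, so the live question for Cohort B is whether escalation is open.

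**2. Whether the suspension rule settles it**

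The trigger is a proportion above 1/3. Since 2/6 = 1/3, a count of 2 of 6 does not trigger it. Two failures earlier on would: 2/3, 2/4 and 2/5 all exceed 1/3. A suspension need not end accrual, however, because the review may close "with possible determinations to continue at the specified dose level in all three cohorts". The cohort can then reach six patients with two failures and face the same question.

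**3. How often the disputed count would arise**

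Let X be the number not successfully treated among 6, taken as Binomial(6, p). The documents give no failure rate for Cohort B at DL1, so p is an assumption shown over a range.

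- P(X = 0) = (1−p)^6
- P(X = 1) = 6p(1−p)^5
- P(X = 2) = 15p²(1−p)^4

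At p = 0.20:

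- P(X = 0) = 0.8^6 = 0.262
- P(X = 1) = 6 × 0.2 × 0.8^5 = 0.393
- P(X = 2) = 15 × 0.04 × 0.8^4 = 0.246
- P(X ≤ 1) = 0.655 and P(X ≤ 2) = 0.901

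| Assumed p | P(X ≤ 1) | P(X ≤ 2) | P(X = 2) |
|---|---|---|---|
| 0.10 | 0.886 | 0.984 | 0.098 |
| 0.20 | 0.655 | 0.901 | 0.246 |
| 1/3 | 0.351 | 0.680 | 0.329 |

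The last column is both the chance of landing on the disputed count and the gap between the two rules in the chance of qualifying for DL2.

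**The case against.** The strongest answer is that neither sentence orders anything. The Cohort B sentence is permissive, the general one only puts escalation under consideration, and the design is declared non-prescriptive. Section 9.2 also shows the committee acting outside any six-patient count: it took Cohort B down electively after 2 patients. Nobody is obliged to escalate at 2 of 6, and a cautious committee could require both conditions, which amounts to at most 1 of 6. This stands, and it limits the practical effect. It does not say which count opens the question.

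One could also argue that the specific Cohort B sentence overrides the general one. That is a reasonable reading, but no visible text says so, and the general paragraph expressly covers each cohort and dose level. Section 4.0 points to sections 2.4.1 and 2.4.2 for experience to date. Those sections are not in the copy reviewed, so the reasoning behind the Cohort B figure may lie there.

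A reader might infer three stronger points, which the documents do not support:

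- **That Cohort A shows at most 2 of 6 to be too lax.** Section 9.2 says that "the original design criteria for escalation to DL2" were satisfied at that threshold, and later that "Cohort A was dose de-escalated to DL1 given the development of two DLTs at DL2". It does not give Cohort A's DL1 count. If that count was 0 or 1, both rules would have allowed escalation.
- **That the Cohort B figure is a leftover from the original design.** This is possible, since the original Cohort A criterion uses the same number, but nothing visible states it.
- **That Cohort C has the same conflict.** At 2 of 6, Cohort C stays open at DL2 under its own paragraph while de-escalation is considered under the general one. Those two can hold together.

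**Conclusion.** The inconsistency is real and sits in current operative text: two counts for one decision, on the same endpoint and the same six patients. It matters only at exactly 2 of 6. That result has probability 10%, 25% and 33% at failure rates of 0.10, 0.20 and 1/3. These figures rest on the assumed rates and on independent outcomes with a common failure probability.

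Either threshold alone would be a legitimate design. A reader should not infer that the plan compels a return to DL2 at 2 of 6, because the study committee decides under either wording. The point is worth correcting because it concerns the stated condition for a dose increase in children and is cheap to settle.

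**What to change.** In the Cohort B paragraph of section 9.2, change the re-escalation condition from at most 2 of 6 to at most 1 of 6, to match the general paragraph. This is the cautious choice after one hepatic DLT and one near-DLT in the 2 patients at DL2. It needs no extra patients or procedures. Its cost is a lower chance of qualifying to test DL2 again: 66% instead of 90% at a 20% failure rate, 89% instead of 98% at 10%, and 35% instead of 68% at one third.

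If the committee and the DSMC intend at most 2 of 6 for Cohort B, keep that figure and add a sentence to the general paragraph saying that the Cohort B condition governs its re-escalation.

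Leave the Cohort C threshold and the general counts as they are. Changing either would alter the rules for other cohorts, which this point does not justify.

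### The expansion boundary in section 9.2 (2 of 5, then 3 of 6) matches its own Bayesian criterion only if Phase I had no failures; after 1 of 6 it misses a cohort that already meets the criterion

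*Combined protocol and SAP*

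**What the plan says.** Section 9.2 (Study Design) treats a failure rate above 10% as unacceptable. Its Bayesian rule with a Beta(1,4) prior "will be used to judge the empirical evidence from both the Phase I and expansion" cohorts. The threshold is "A posterior probability of greater than 80% that" the rate exceeds 0.10.

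The same paragraph turns this into counts: "this criterion will be satisfied if 2 or more of the first 5 evaluable patients in the expansion cohort experience a treatment failure", and subsequently "if 3 or more of the first 6 evaluable patients have a treatment failure". No condition on the Phase I result is attached. When the criterion is met, "the study will be suspended to accrual pending review of toxicities by the study committee, in consultation with the Data and Safety Monitoring Committee".

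Section 9.0 sets 6 evaluable patients for Phase I and 6 more for expansion, so at most 12 per cohort and dose level.

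On the Phase I result, section 9.2 considers escalation "when no more than 1 patient is treated unsuccessfully after the first 6 evaluable patients have been enrolled", while "the decision to de-escalate will be considered separately for each cohort and dose level when more than 1 patient is treated unsuccessfully". Elsewhere the section keeps Cohort C open at DL2, and allows Cohort B to be re-escalated, with up to 2 of 6 not successfully treated. A separate running rule suspends the study if more than one third of evaluable patients fail, within a cohort or over all cohorts.

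**The concern.** A posterior based on Phase I plus expansion data depends on the Phase I failures. One boundary that counts expansion failures only cannot be right for every Phase I result. The study committee will apply the counts, because they are the only operational form given. If they are too lenient for an ordinary Phase I result, a cohort whose data already meet the protocol's own threshold goes on accruing without the suspension and the consultation with the Data and Safety Monitoring Committee (DSMC) that section 9.2 attaches to that threshold.

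**Working it through.** **Inputs.** Prior Beta(1,4), limit 0.10, cut-off 0.80, cumulative data (section 9.2); 6 Phase I and 6 expansion patients (section 9.0).

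**Formula.** With x failures in n patients the posterior is Beta(1 + x, 4 + n − x). For this prior, P(p > 0.10) equals the probability that a Binomial(n + 4, 0.10) count is at most x. Example, 2/11: 0.9^15 + 15 × 0.1 × 0.9^14 + 105 × 0.01 × 0.9^13 = 0.206 + 0.343 + 0.267 = 0.816.

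**Reproducing the printed counts (Phase I 0/6).**

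| Expansion | Total | Posterior | Above 0.80? |
|---|---|---|---|
| 1 of 5 | 1/11 | 0.549 | no |
| 2 of 5 | 2/11 | 0.816 | yes |
| 2 of 6 | 2/12 | 0.789 | no |
| 3 of 6 | 3/12 | 0.932 | yes |

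This is exactly the printed rule, including the step from 2 to 3.

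**Phase I 1/6.** The posterior before expansion is 0.736. One expansion failure then gives:

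| Expansion patients | 1 | 2 | 3 | 4 | 5 | 6 |
|---|---|---|---|---|---|---|
| Total | 2/7 | 2/8 | 2/9 | 2/10 | 2/11 | 2/12 |
| Posterior | 0.910 | 0.889 | 0.866 | 0.842 | 0.816 | 0.789 |

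The criterion is met with 1 failure in the first 5; the counts ask for 2. At patient 6, two failures (3/12 = 0.932) meet it; the counts ask for 3. The one-third rule within the cohort does not fire either: 2/7 is 29% and 2/11 is 18%.

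**Phase I 2/6.** The posterior is 0.930, so the criterion is met before any expansion patient is treated.

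**Other readings.**
- Expansion data only: 1 of 4 (0.813) and 2 of 6 (0.930) already trigger, so the counts do not fit.
- Three cohorts pooled, 18 Phase I patients: 2 of 5 fits only after 2/18 (3/23 = 0.718, 4/23 = 0.873), and then 2 of 6 already triggers (4/24 = 0.858).
- A different cut-off: the counts imply one between 0.789 and 0.816 after 0/6, but between 0.932 (3/12) and 0.944 (3/11) after 1/6. The ranges do not overlap.

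**Size after 1/6.** The printed counts trigger with at least 2 failures in the first 5: 1 − (1−p)^5 − 5p(1−p)^4. The 3-of-6 clause adds nothing, since 3 of 6 implies at least 2 of the first 5. The criterion triggers with at least 1 failure in the first 5: 1 − (1−p)^5. The difference is 5p(1−p)^4. The chance of a 1/6 start is 6p(1−p)^5.

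| True failure rate p | 10% | 25% | 37.5% |
|---|---|---|---|
| Review called, printed counts | 8% | 37% | 62% |
| Review called, stated criterion | 41% | 76% | 90% |
| Difference | 33% | 40% | 29% |
| Chance of a 1/6 start | 35% | 36% | 21% |
| 1/6 start and missed review | 12% | 14% | 6% |

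Adding the within-cohort one-third rule to the printed counts changes none of these figures. The rates are illustrative; 37.5% is the 6/16 delay rate that section 2.3 gives for second or greater relapse.

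**The case against.** **The counts can be read as sufficient, not exclusive.** The text says the criterion will be satisfied if the counts are reached, and in every 6-patient Phase I case above it is. A statistician applying the posterior itself would flag one failure after 1/6. That is true, but the sentence is offered as the operational form, and it is silent when the stated criterion is met.

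**The consequence is limited.** The rule pauses accrual for a review that may let the study continue unchanged. Dose-limiting toxicities are reported immediately (section 4.2), safety meetings are held weekly as needed (12.2), the DSMC meets every six months (12.3), the toxic-death rule stands (9.5), and section 9.2 already provides that "Accrual to the study will be halted, before reopening for expansion, once at least 6 evaluable patients have been treated" at the final dose level in each cohort. All of this stands. What is lost is the specific suspension and consultation at the time the threshold is crossed.

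**Other Phase I totals also fit the counts.** Totals of 1/14 or 2/22 reproduce the printed pattern, and pooled Phase I accrual could exceed 18. Each of these again depends on one particular Phase I result that the plan does not state.

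**At a true rate of 10% a missed review is arguably no loss,** because the rate does not exceed the limit. This is fair: the 12% in that column is better read as a pause avoided. The 37.5% rate is also a delay rate for standard therapy, with a 95% interval of 15% to 65%, and not this trial's endpoint.

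**The Phase I counts may be known.** Section 4.0 refers to sections 2.4.1 and 2.4.2 for experience to date, which were not in the text available. If a cohort had 0/6 at its expansion dose level, the printed rule is exact there.

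**Conclusion.** The concern holds. At the planned Phase I size of 6, the printed boundary agrees with the stated criterion only after 0/6. After 1/6, a result that section 9.2 treats as compatible with escalation, the boundary is one failure too lenient throughout, and the chance of calling the review falls by 29 to 40 percentage points at the rates examined. After 2/6 the criterion is met on entry. There the practical gap is smaller, because section 9.2 separately considers de-escalation and halts accrual before expansion; but the counts and the criterion disagree, and that step mentions no DSMC consultation.

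This rests on reading the rule per cohort and dose level with 6 Phase I patients, and on independent outcomes with a constant failure rate for the probabilities. Which Phase I result applies to each cohort cannot be settled from the text available. Cohort A now enrolls at DL1 only, where the original design allowed escalation with up to 2/6 failures, so a nonzero count there cannot be excluded. A suspension threshold that contradicts its own definition should be corrected.

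**What to change.** Make the criterion and the counts agree.

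- **If the 0.80 cut-off is intended,** state the boundary on total failures per cohort and dose level, Phase I plus expansion: met at 2 or more among 6 to 11 evaluable patients, or 3 or more among 12. By Phase I result this is 2 of the first 5 or 3 of 6 after 0/6; 1 of the first 5 or 2 of 6 after 1/6; and met on entry after 2/6. Say that the current counts apply only after 0/6.
- **If the printed counts are intended,** change the cut-off and re-derive the counts for each Phase I result. A new cut-off alone is not enough: 0.94 gives 2 of 5 and 3 of 6 after 1/6, but 3 of 5 and 4 of 6 after 0/6.

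In either case, reconcile the two statements in section 9.2 about a cohort with 2/6 failures (may stay open or be re-escalated; de-escalation considered above 1), and say whether the DSMC is consulted at that point. A small correction can go in at the same time: the 90th percentile of Beta(1,4) is 0.44, and 93% of the prior lies below the printed 0.48. No decision depends on it.

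The cost is a few sentences in section 9.2, with no extra patients or data. Keeping 0.80 means more pauses: after 1/6, 41% rather than 8% when the true failure rate is only 10%. If that is thought too many, the cut-off itself should be reconsidered openly.
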